12.3.1 Descriptive Statistics

General descriptive statistics for numeric variables will include the n (number of observed values), the mean, the standard deviation, the median, the minimum, and the maximum values. For categorical variables, the number and percent of patients with a specific level of the variable will be presented.

12.3.2 Missing data

Details on dealing with missing data, along with the handling of possible outliers, will be described in the SAP. Other critical missing data, if any, will be discussed during the review of the data before database lock and decisions will be fully documented in the Data Review Report.

12.3.3 Patient demographics and baseline characteristics

Demographics and baseline variables will be summarized separately in each cohort by treatment group using descriptive statistics for the ITT population.

12.3.4 Primary efficacy variable

Number of ventilator-free days during the **21 days** after randomisation will be compared between groups by using an ANOVA model including treatment group, age and country as factors. Patients who die or are mechanically ventilated longer than this period are assessed as zero ventilator-free days.

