12. STATISTICAL METHODS

12.1 Sample Size

A total of 70 patients will be randomised in the study with a ratio 3:2 (i.e. 42 patients randomised to the poractant alfa group and 28 in the control group). Assuming patients in the control arm being free from ventilation on average 1 week (i.e. 7 days), this sample size achieves 84% power to detect a difference of 4 days (i.e. on average 11 ventilation-free days for patients treated with poractant alfa), assuming a standard deviation of 5.5 and a two-sided significance level (alpha) of 0.05 using a two-sample t-test.

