12.3.5 Secondary efficacy variables

- Number of days alive and free from ventilation at **Day 28**, number of days alive and free from invasive and non-invasive ventilation at **Day 21** and **Day 28** will be compared between groups by using an ANOVA model including treatment group, age and country as factors.
- Mortality at Day 21 and Day 28 will be compared by groups using logistic regression including treatment group, age and country as factors. Difference in the proportions and related 95% confidence interval will be estimated from the model.
- Percentage of patients with improvement in severity status defined as a decrease in the

Clinical Study Code No.: CLI-050000-04	Version No.: 4.0
EUDRACT No.: 2020-002632-75 – IND No: 153286	Date: 02 MAR 2021

severity score at Day 28 or Discharge, whichever comes first, will be compared by groups using logistic regression including treatment group, age and country as factors. Difference in the proportions and related 95% confidence interval will be estimated from the model.

- Change from baseline in PaO₂/FiO₂ at 6 and 12 hours after each treatment and relative timepoints in the control group will be compared between groups using an ANCOVA model including group, age and country as fixed effect and baseline value as covariate. The same analysis will be performed at each additional timepoint.
- Percentage of patients alive and with PaO₂/ FiO₂ improvement of >20% at **6 and 12 hours following administration of each dose** in the treated group and at similar timepoints in the control group will be compared by groups using logistic regression including treatment group, age and country as factors. Difference in the proportions and related 95% confidence interval will be estimated from the model. Patients who die are considered as a failure. The same analysis will be performed at each additional timepoints.
- Change from baseline in FiO₂ will be analysed as PaO₂/FiO₂.
- Length of ICU stay (in days) at **Day 28** will be compared between groups using ANOVA model including group, age and country as fixed effect. Patients who die or are mechanically ventilated longer than this period are assigned with 28 days.
- Percentage of patients alive and out of ICU at **Day 28** using logistic regression including treatment group, age and country as factors. Difference in the proportions and related 95% confidence interval will be estimated from the model.

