7.5 Covariates

Not applicable. All data will be summarized by means of descriptive statistics.

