8.2.3 Other Baseline and Disease Characteristics

The following baseline and disease characteristics parameters will be summarised using descriptive statistics by treatment group and overall based on ITT Set:

- Vital signs (systolic blood pressure (SBP), diastolic blood pressure (DBP), and pulse rate) at baseline;
- Ventilatory parameters at baseline (PaO₂/FiO₂ ratio and FiO₂);
- SOFA score at baseline.

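### The protocol's primary model for ventilator-free days has no baseline severity term, so some precision may go unused; one pre-named PaO2/FiO2 covariate would be a cheap, optional gain

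*Protocol*

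**What the plan says.** Protocol 12.3.4 has the primary endpoint "compared between groups by using an ANOVA model including treatment group, age and country as factors". Section 12.3.4.1 uses the same three terms in the logistic model for the key secondary endpoint.

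Baseline severity data are planned for everyone. PaO2/FiO2 below 150 mmHg is an inclusion criterion (4.2), and SOFA is on the screening schedule for both arms (7.1). SAP 8.2.3 tabulates baseline PaO2/FiO2 and "SOFA score at baseline".

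The protocol does adjust for a baseline value in some places. Change in PaO2/FiO2 is analysed "using an ANCOVA model including group, age and country as fixed effect and baseline value as covariate" (12.3.5), and changes in FiO2 and SOFA are treated the same way.

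The power statement is that "this sample size achieves 84% power to detect a difference of 4 days", "assuming a standard deviation of 5.5 and a two-sided significance level (alpha) of 0.05 using a two-sample t-test" (12.1).

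The final SAP withdrew all these models because the trial closed before reaching 70 patients (section 12). Its entry for covariates (7.5) reads "Not applicable. All data will be summarized by means of descriptive statistics", and 9.1 only describes the primary endpoint by group.

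**The concern.** How sick a patient is at entry plausibly predicts both time on the ventilator and death. The protocol's own severity scale (section 8) is built on PaO2/FiO2, with death as its last grade. Randomisation is stratified by site only (6.5), so the design does not balance severity. In a small trial the arms can differ in severity by chance. A baseline covariate that predicts outcome removes that part of the noise and narrows the interval for the treatment difference.

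What is at stake is efficiency: a somewhat wider interval than the collected data would allow, and a raw difference in means that partly reflects who happened to be sicker at entry.

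**Working it through.** **Inputs from Protocol 12.1.** 42 and 28 patients ("A total of 70 patients will be randomised in the study with a ratio 3:2"), a difference of 4 days, SD 5.5, two-sided alpha 0.05.

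**Input not in the documents.** R², the share of outcome variance that baseline severity explains beyond age and country. I assume 0 to 0.20.

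**Step 1: reproduce the stated power.**
- SE = 5.5 × √(1/42 + 1/28) = 5.5 × 0.2440 = 1.342 days.
- Noncentrality = 4 / 1.342 = 2.98.
- Noncentral t with 68 df gives 83.6%; the normal approximation gives 84.6%. The stated 84% is met with no covariate.
- With age (linear) and country (two levels) in the model, df = 70 − 4 = 66 and power is still 83.6%. SAP section 12 also mentions Italy; a third country would cost one more df.

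**Step 2: add baseline severity.** Residual SD = 5.5 × √(1 − R²). One covariate leaves 65 df and two leave 64. At the same R² the two powers differ by less than 0.1 point. The table uses 64 df.

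| Assumed R² | Residual SD | SE (days) | 95% CI half-width (days) | Power | Equivalent unadjusted N = 70/(1 − R²) |
|---|---|---|---|---|---|
| 0 | 5.50 | 1.34 | 2.68 | 83.5% | 70 |
| 0.05 | 5.36 | 1.31 | 2.61 | 85.4% | 74 |
| 0.10 | 5.22 | 1.27 | 2.54 | 87.2% | 78 |
| 0.20 | 4.92 | 1.20 | 2.40 | 90.7% | 88 |

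**Step 3: the full cost of a covariate.** The table charges only for degrees of freedom. Chance imbalance in q covariates also inflates the variance of the treatment estimate, by an expected factor of about 1 + q/(residual df − 1).
- One covariate at N = 70: 1 + 1/64 = 1.016. Power becomes 83.0%, 84.8%, 86.7% and 90.3% at R² of 0, 0.05, 0.10 and 0.20. The SE breaks even at R² = 1 − 1/1.016, about 1.5%.
- Two covariates at N = 70: 1 + 2/63 = 1.032. Power becomes 82.4%, 84.3%, 86.1% and 89.8%.

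**Step 4: a small final sample.** The documents do not give the final N, so take 20 patients (12 and 8) as an illustration. With age and country only (16 df), power is 32%.
- Two covariates: 14 df, factor 1 + 2/13 = 1.154. Power is 31% at R² 0.10 and 34% at 0.20.
- One covariate: 15 df, factor 1 + 1/14 = 1.071. Power is 33% and 36%.

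**Step 5: how far chance imbalance in severity moves the raw difference at N = 70.** Its standard error is √R² × 1.342: 0.30, 0.42 and 0.60 days at R² of 0.05, 0.10 and 0.20. Multiplied by 1.96, the 95% bounds are ±0.6, ±0.8 and ±1.2 days, against a target of 4. The unadjusted SE already contains this variation.

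**The case against.** Much of the case against stands.

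- **Validity and power.** A reader might infer that leaving out severity biases the comparison or undermines the 84%. The documents do not support that. Allocation is randomised, and the power calculation uses an unadjusted t-test that Step 1 reproduces.
- **Consistency.** A reader might infer that the protocol contradicts itself by adjusting secondary endpoints but not the primary one. Only the change-from-baseline endpoints are adjusted for their own starting value. The other modelled secondary endpoints, such as mortality and ICU stay, use treatment, age and country, as the primary does. Ventilator-free days have no baseline value of their own.
- **Size of the gain.** No figure links PaO2/FiO2 or SOFA to ventilator-free days. Eligibility restricts the range of PaO2/FiO2, and PaO2/FiO2 is a component of SOFA, so the two gains would overlap. Both facts point to the lower end of the table.
- **Cost.** It is tempting to call adjustment free. Steps 3 and 4 show that it is cheap at 70 patients but may not pay at 20. The schedule's footnote on SOFA foresees components missing before randomisation and accepts data from the previous 24 hours. SAP 7.4 generally does not impute, so a patient without a baseline value would drop out of the model.
- **Superseded model.** The final SAP fits no model, and editing Protocol 12.3.4 alone would change no planned output.

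The omission itself remains, and so does its low cost of repair at the planned size. The SAP still opens section 9 by speaking of comparisons between groups, and readers will compare the two raw means.

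**Conclusion.** The point holds as a modest efficiency suggestion. The primary linear model could carry one severity covariate that eligibility already requires. At the planned size this would raise power by roughly 2, 4 or 7 points at R² of 0.05, 0.10 or 0.20, and slightly less (about 1, 3 or 7) once chance covariate imbalance is counted. If severity predicts nothing, the loss is about half a point or less.

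These figures rest on the protocol's SD of 5.5, on age entering linearly with two countries, and on R² values that are assumed. They cover the linear model only; nothing here quantifies a gain for the key secondary logistic model. At about 20 patients the benefit is small or absent, and two covariates can lose power.

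**What to change.** - **Protocol 12.3.4:** add baseline PaO2/FiO2 as one pre-named continuous covariate. Add baseline SOFA only if the analysed sample is near 70.
- **Protocol 12.3.4.1:** do not put both measures into the logistic model when events are few, because sparse data can make its estimates unstable.
- **SAP 7.5 and 9.1:** if a between-group estimate is reported despite the move to descriptive statistics, give the adjusted difference with its 95% CI as a supportive result next to the descriptive table. State how many patients were left out for a missing baseline value.

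The cost is 1 df (2 with SOFA) and the loss from the model of any patient without a baseline value. No new data are needed. In the protocol this is a change of wording. In the SAP it means bringing back a model, so section 12, section 14 and the table list would need matching edits.

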12.3.4.1 Key secondary variable

Percentage of patients alive and free of respiratory failure (i.e., need for mechanical ventilation, ECMO, non-invasive ventilation, or high-flow nasal cannula oxygen delivery) at **Day 28** will be analysed using logistic regression including treatment group, age and country as factor. Difference in the proportion and related 95% confidence interval will be estimated from the model.

12.3.5 Secondary efficacy variables

- Number of days alive and free from ventilation at **Day 28**, number of days alive and free from invasive and non-invasive ventilation at **Day 21** and **Day 28** will be compared between groups by using an ANOVA model including treatment group, age and country as factors.
- Mortality at Day 21 and Day 28 will be compared by groups using logistic regression including treatment group, age and country as factors. Difference in the proportions and related 95% confidence interval will be estimated from the model.
- Percentage of patients with improvement in severity status defined as a decrease in the

Clinical Study Code No.: CLI-050000-04	Version No.: 4.0
EUDRACT No.: 2020-002632-75 – IND No: 153286	Date: 02 MAR 2021

severity score at Day 28 or Discharge, whichever comes first, will be compared by groups using logistic regression including treatment group, age and country as factors. Difference in the proportions and related 95% confidence interval will be estimated from the model.

- Change from baseline in PaO₂/FiO₂ at 6 and 12 hours after each treatment and relative timepoints in the control group will be compared between groups using an ANCOVA model including group, age and country as fixed effect and baseline value as covariate. The same analysis will be performed at each additional timepoint.
- Percentage of patients alive and with PaO₂/ FiO₂ improvement of >20% at **6 and 12 hours following administration of each dose** in the treated group and at similar timepoints in the control group will be compared by groups using logistic regression including treatment group, age and country as factors. Difference in the proportions and related 95% confidence interval will be estimated from the model. Patients who die are considered as a failure. The same analysis will be performed at each additional timepoints.
- Change from baseline in FiO₂ will be analysed as PaO₂/FiO₂.
- Length of ICU stay (in days) at **Day 28** will be compared between groups using ANOVA model including group, age and country as fixed effect. Patients who die or are mechanically ventilated longer than this period are assigned with 28 days.
- Percentage of patients alive and out of ICU at **Day 28** using logistic regression including treatment group, age and country as factors. Difference in the proportions and related 95% confidence interval will be estimated from the model.
- Delta SOFA Score and sub-score components at **Day 3 and Day 28 or Discharge**, whichever comes first, will be analysed at each timepoint using ANCOVA model including group, age and country as fixed effect and baseline value as covariate.
- Percentage of patients alive and organ failure free (SOFA score=0) at **Day 28 or Discharge**, whichever comes first will be compared by groups using logistic regression including treatment group, age and country as factors. Difference in the proportions and related 95% confidence interval will be estimated from the model.
- Change from baseline in ventilator parameters (TV, RR, C_{dyn}, C_{stat}, PEEP, PIP, P_{plat}) will be summarized by means of descriptive statistics or frequency distribution, as appropriate by group at each timepoint.
- Change from baseline in BGA acid-base balance parameters (i.e. pH, pCO₂, pO₂, HCO₃, lactate) will be summarized by means of descriptive statistics by group at each timepoint.

12.3.6 Exploratory Efficacy Variables

Exploratory parameters from TA aspirates and blood samples will be summarized only in the subgroup of UK patients both as absolute values and as change from baseline values by treatment group at each timepoint using descriptive statistics.

12.3.7 Safety variables

Adverse Events

The number of patients who experienced at least one AE, AEs related to poractant alfa (treated group) (ADRs), serious AEs (SAEs) and AEs leading to death will be summarized by group. Summaries will be presented overall (number and percentage of patients having at least one event, total number of events) and by system organ class and preferred term (number and percentage of patients having at least one occurrence of that event).

Clinical Study Code No.: CLI-050000-04	Version No.: 4.0
EUDRACT No.: 2020-002632-75 – IND No: 153286	Date: 02 MAR 2021

All adverse events will be listed.

Vital Signs

Vital sign values and their change from baseline will be summarized by group at each timepoint using descriptive statistics.

Laboratory data

Laboratory parameters and their change from baseline will be summarized by group at each timepoint using descriptive statistics.

All laboratory data will be listed.

12.3.8 Interim analysis

Interim analysis not planned.

13. ETHICS COMMITTEE/INSTITUTIONAL REVIEW BOARD APPROVAL

The study proposal will be submitted to the Research Ethics Committee/HRA/MHRA and IRB/FDA in accordance with the requirements in England and US.

The REC//HRA/MHRA and IRB/FDA shall give its opinion in writing -clearly identifying the study number, study title and informed consent form approved-, before the clinical trial commences.

A copy of all communications with the REC/HRA and IRB will be provided to the Sponsor.

The Investigator should provide written reports to the REC/HRA/MHRA and IRB annually or more frequently if requested on any changes significantly affecting the conduct of the trial and/or increasing risk to the patients (according to the requirements of each country).

14. REGULATORY REQUIREMENTS

The study will be notified to the Health Authorities (or authorized by) according to the legal requirements in each participating country.

Selection of the patients will not start before the approval of the Ethics Committee/Institutional Review Board has been obtained and the study notified to Health Authorities (or authorized by).

15. INFORMED CONSENT

It is the responsibility of the Investigator to obtain informed consent/eConsent for each patient before performing any trial related procedure by using the latest REC/HRA or IRB approved version of the document.

It is not expected that patients considered for enrolment in this study will have the capacity to consent to take part due to the nature of the underlying disease process, as they will be under sedation and will be mechanically ventilated.

Regarding UK sites, if the patient is incapable of giving informed consent, consent should be sought from the patient's personal legal representative. This person must not be connected with the conduct of the trial and must be suitable to act as the legal representative by virtue of their relationship with the patient and is available and willing to do so (e.g. a friend or relative). In the case that the patient's personal legal representative is not available to provide consent, without a delay that would, in the opinion of the Investigator, compromise the potential life-saving effect of the study treatment, the

Clinical Study Code No.: CLI-050000-04	Version No.: 4.0
EUDRACT No.: 2020-002632-75 – IND No: 153286	Date: 02 MAR 2021

consent should be sought from a professional legal representative. This person is identified, according to the UK regulations, as a person not connected with the conduct of the trial, who may be the doctor primarily responsible for the medical treatment of the patient or a person nominated by the institution. Regarding USA sites, if the patient is incapable of giving informed consent it must be obtained from their legally authorized representatives.

For both the USA and UK population, if a patient is consented to the study by a third party (according to the requirements set out in this section above) and they regain capacity, it is expected that the participant is informed and provides their consent to continue participation in the trial.

This consent from the patient to remain in the study from the patient should be sought as soon the condition of the patient will allow it.

The same procedure applies to processing of personal data of the patient and providing of consent to the processing of personal data according to the European Regulation n. 2016/679 on the Protection of Personal Data, the Personal Data Protection Act 2018 and subsequent amendments and additions, the provisions and guidelines of the National Data Protection Authorities, as well as any other applicable data protection laws and regulations.

Each patient's or acceptable third party's signed informed consent(s) must be kept on file by the Investigator. One copy must be given to the patient or the person consenting on their behalf.

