4.4 Patient Withdrawals

Patients must be discontinued from the study for any of the following reasons:

- The patient or the patient’s representative withdraws the consent
- The patient is lost to follow-up.
- The sponsor or the regulatory authorities or the Ethics Committee(s), for any reason, terminates the entire study, or terminates the study for this trial site or this particular patient.

It is understood by all concerned that an excessive rate of withdrawals can render the study uninterpretable.

Should a patient withdraw from the study, all efforts will be made to complete and report the observations as thoroughly as possible.

Patient who discontinues study treatment should not be considered automatically withdrawn from the study (except if the reason is consent withdrawal or lost to follow up). The investigator and study staff must discuss with the patient (or with the patient’s representative) asking to continue attending the remaining study visits even though the treatment has been terminated prematurely.

In case of withdrawal, the Investigator must fill in the “Study Termination” page in the CRF reporting the main reason for withdrawal.

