6.3 Other Populations Defined for Tables and Listings

For the purposes of tables and listings the following population is defined:

- Enrolled Set: all subjects who have a signed informed consent for the study.

Note: the informed consent can be signed by subject himself when feasible or, in case of unconscious subject, by a third party (legal representative or by the physician only) according to the local regulations and the pre-defined rules suitable for a trial conducted at Intensive Care Units. In case the subject is consented to the study by a third party and they regain capacity, the participant was informed and their consent was requested to continue the participation in the trial.

7 General Considerations for Statistical Analysis

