7.4 Handling of Missing Data

In general, except as described below, missing data will not be imputed.

The number of subjects with missing data will be presented under a “Missing” category. Unless otherwise stated, missing values will not be included in the denominator count when calculating percentages.

When quantitative variables are being summarized, only the non-missing values will be evaluated for calculating summary statistics.

Other critical missing data, if any, will be discussed during the review of the data before database lock. Decisions will be fully documented in the Data Review Report.

Medications: Missing/Incomplete Date

In case of missing or incomplete dates not directly allowing allocation to any category of medications, a worst-case allocation will be done according to the available parts of the start and the stop dates. The medications will be allocated to the first category allowed by the available data, according to the following order:

1. Concomitant medication;
2. Maintained medication;
3. Prior medication.

Procedures: Missing/Incomplete Date

In case of missing or incomplete dates not directly allowing allocation to any category of procedure, a worst-case allocation will be done according to the available parts of the start and the stop dates. The procedure will be allocated to the first category allowed by the available data, according to the following order:

1. Concomitant procedure;
2. Maintained procedure;
3. Prior procedure.

Adverse Events (AEs): Missing/Incomplete Date

In case of missing or incomplete date/time not directly allowing allocation to any of the category of AEs, a worst-case allocation will be done according to the available parts of the start and the stop dates/times. The AE will be allocated to the first category allowed by the available data, according to the following order:

1. Treatment emergent;
2. Pre-treatment.

Adverse Events (AEs): Missing Severity

In case of missing severity, the severity will not be imputed and will be reported as “Missing”. For the table of TEAEs by maximum severity, the maximum severity will be considered as the maximum of the non-missing severities for the relevant subject and preferred term.

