9.2 Key Secondary Efficacy Variable

The key secondary efficacy variable is the percentage of subjects alive and free of respiratory failure (i.e., need for mechanical ventilation, ECMO, non-invasive ventilation, or high-flow nasal cannula oxygen delivery) at **Day 28**.

Notes:

The subject will be defined alive and free of respiratory failure if:

- On Patient Status form at “D28-FU” visit, the subject is still alive

AND

- On Ventilatory Support form, if start date is not missing, max (end date) for any ventilator type > date of “D28 – FU” visit

The percentage will be summarized.

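### Patients who wake and decline to continue come mainly from the better outcomes, and the Day 28 rules in SAP 9.2, 9.3.9 and 7.4 score them as non-successes or drop them

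*Protocol*

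**What the plan says.** **Consent.** Protocol 15 states: "It is not expected that patients considered for enrolment in this study will have the capacity to consent to take part". Entry is therefore normally on the consent of a legal representative. When a third-party-consented patient regains capacity, "it is expected that the participant is informed and provides their consent to continue participation in the trial". SAP 6.3 puts it more softly: "the participant was informed and their consent was requested to continue the participation in the trial". On data, Protocol 15 adds: "The same procedure applies to processing of personal data of the patient".

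**Withdrawal.** Protocol 4.4 begins its list with "Patients must be discontinued from the study for any of the following reasons", and the first reason is "The patient or the patient’s representative withdraws the consent". A patient who only stops treatment stays in follow-up, but consent withdrawal is an explicit exception. For withdrawn patients there is one general sentence promising every effort to complete the observations. Chart review or a call to the treating physician is described in Protocol 3.2 only for transferred patients who remain in the study.

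**Scoring.** Neither document says how a refuser is scored, and consent withdrawal is not among the intercurrent events (Protocol 12.3, SAP 7.2).
- SAP 9.2 (alive and free of respiratory failure) requires the Patient Status form to show that at the Day 28 "visit, the subject is still alive". SAP 9.3.9 (alive and out of ICU) has the same requirement.
- SAP 7.4 says that, by default, "missing values will not be included in the denominator count when calculating percentages". It also provides a Missing category in the tables.
- SAP 9.3.2 (mortality) has no rule for unknown vital status.
- SAP 9.3.1 and 9.3.3 derive ventilator-free days from the last ventilation end date.
- SAP 9.3.11 accepts a missing death date as meeting the alive condition.

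**The concern.** Re-consent is put only to patients well enough to be asked. Someone who dies or stays sedated is never asked, so loss of Day 28 data through re-consent is related to outcome. Take a patient extubated and awake by Day 12 who declines to continue. If no Day 28 form exists, that patient does not meet the definition of success in SAP 9.2 or 9.3.9. If treated as missing, the patient leaves the denominator while every known death remains. Both routes understate Day 28 success, and dropping refusers also overstates Day 28 mortality.

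The same patient may be credited with ventilator-free days and meet the alive condition in SAP 9.3.11, so different tables could score one person in opposite directions. The key secondary endpoint is among those affected. Because the trial is open-label, refusal could also differ between arms.

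**Working it through.** **Inputs.** The documents give no refusal rate, so the plan has no figure of its own to reproduce on this point. Mortality of 30–70% is the ICU range in Protocol 1.1. The refusal rate *w* among survivors is assumed at 5%, 10% and 20%. Planned numbers are 42 and 28 (Protocol 12.1).

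**Simplifications.** All refusers decline before the Day 28 visit, have no Day 28 form, and are truly alive at Day 28. Survival stands in for success; the same formulas apply to any Day 28 success percentage *s* if only true successes refuse.

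**Formulas**, with *s* = true percentage and *m* = 1 − *s*:
- counted as failures: *s*(1 − *w*)
- dropped: *s*(1 − *w*) / (1 − *s·w*)
- mortality with refusers dropped: *m* / (1 − *s·w*)

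Example, *s* = 0.70, *w* = 0.10: failures 0.70 × 0.90 = 63.0%; dropped 0.63 / 0.93 = 67.7%; mortality 0.30 / 0.93 = 32.3%.

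**Within one arm, true survival 70 / 50 / 30%**

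| Refusal *w* | Failures (%) | Dropped (%) | Mortality if dropped (%) |
|---|---|---|---|
| 5% | 66.5 / 47.5 / 28.5 | 68.9 / 48.7 / 28.9 | 31.1 / 51.3 / 71.1 |
| 10% | 63.0 / 45.0 / 27.0 | 67.7 / 47.4 / 27.8 | 32.3 / 52.6 / 72.2 |
| 20% | 56.0 / 40.0 / 24.0 | 65.1 / 44.4 / 25.5 | 34.9 / 55.6 / 74.5 |

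**Between arms, equal refusal**, assumed true success 65% vs 50% (15.0 points):
- *w* = 10%, failures: 58.5 − 45.0 = 13.5 points; dropped: 0.585/0.935 − 0.45/0.95 = 62.6 − 47.4 = 15.2 points.
- *w* = 20%: 12.0 points (failures) and 15.3 points (dropped).

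**Between arms, refusal in one arm only**, no true difference, true percentage between 30% and 70%:
- *w* = 5%: spurious gap of 1.5–3.5 points (failures) or 1.1–1.3 points (dropped).
- *w* = 10%: 3.0–7.0 or 2.2–2.6 points.
- *w* = 20%: 6.0–14.0 or 4.5–5.6 points.

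**In patients.** At full planned size, 50% mortality and *w* = 10%, expected refusers are 42 × 0.5 × 0.1 = 2.1 and 28 × 0.5 × 0.1 = 1.4. With 28 controls, 14 truly alive and 2 of them refusing: true 14/28 = 50.0%; failures 12/28 = 42.9%; dropped 12/26 = 46.2%, with mortality 14/26 = 53.8% instead of 50.0%.

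**The case against.** Several points on the other side are good.

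- *A reader might infer that only survivors can be lost this way.* Protocol 4.4 does not support that: a representative may withdraw a patient who never wakes, and a patient who wakes and declines may still die before Day 28. The loss comes mainly, not only, from good outcomes.
- *A reader might infer that every Day 28 rule penalises refusers.* It does not: SAP 9.3.1, 9.3.3 and 9.3.11 can favour them. What stands is inconsistency between tables plus understatement in SAP 9.2 and 9.3.9.
- *A reader might infer that nobody could lawfully obtain Day 28 status.* The consent form was not available for review and may give that permission. What can be said is that Protocol 4.4 and 15 do not state it. That refusing re-consent counts as withdrawal is itself the natural reading, not an explicit rule.
- *A reader might infer that the treatment difference would collapse.* With equal refusal it does not. Large distortion needs refusal to differ by arm, for which the documents give no evidence.
- *The SAP already shows the gap.* The Missing category in SAP 7.4 and the withdrawal reasons by arm in SAP 8.1.2 would let a careful reader bound the result, and critical missing data go to review before database lock. This helps only if refusers are classed as missing; if they are scored as failures under SAP 9.2 or 9.3.9, the percentage itself does not reveal them.
- *Nothing is tested.* SAP 7.5 and section 12 make the final analysis descriptive. That limits the consequence but does not correct the percentages.

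**Conclusion.** The concern holds in a limited form. Outcome-related loss through re-consent is foreseeable from Protocol 15, and the rules that would apply give different answers. Two of those answers, failure under SAP 9.2 and 9.3.9 or exclusion under SAP 7.4, understate Day 28 success.

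At an assumed 10% refusal and 30–70% mortality, the understatement within an arm is 3.0 to 7.0 points if refusers are failures and 2.2 to 2.6 points if they are dropped. Dropping them raises reported mortality by the same 2.2 to 2.6 points. The comparison between arms is fairly robust to equal refusal and vulnerable to unequal refusal.

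These sizes rest on the assumed refusal rate, on refusers being alive at Day 28, and on their Day 28 status being unobtained. The harm is biased descriptive percentages, not an inflated error rate. SAP section 12 records closure before 70 patients, so each refuser weighs more than in the planned sample.

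**What to change.** **SAP 7.4, 9.2, 9.3.2 and 9.3.9 (applies to the existing data).**
- Keep every randomised patient in the denominator. Say so explicitly, because SAP 6.2 restricts the ITT set to patients with post-baseline efficacy data.
- Show Day 28 status unknown as its own category by arm, separate from failure.
- Report the percentage with all unknowns counted as successes and with all counted as failures. In the 28-control example this gives 42.9% to 50.0%.
- If the SAP cannot be reopened, report this as an explained deviation in the clinical study report, which SAP section 1 allows.

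While SAP 9.2 is open, correct its ventilation condition too. As printed, it asks for a ventilation end date later than the Day 28 visit, which appears reversed. That is a separate defect, and the calculations above assume the intended direction.

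**Protocol 4.4 and 15 (for continued or repeat use).** State that a patient who declines may stop study procedures only. Ask separately for permission to keep data already collected and to take Day 21 and Day 28 vital and ventilatory-support status from medical records. With recruitment closed, this cannot recover status already lost.

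**Cost.** A few extra rows in Tables 14.2.2, 14.2.4 and 14.2.12; for the protocol part, consent wording with ethics notification and a slightly longer re-consent discussion.
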